9.3.3.1 Adverse Events

For analysis purpose, AEs in FA will be classified as TEAE during the Part 2 Safety Period and Post-treatment AEs, defined as follows:

TEAE during the Part 2 safety period: any AE that worsened (either in severity or seriousness) or that was newly developed at or after the first dose date of study drug in Part 2 through the end of the Part 2 Safety Period.

Post-treatment AE: any AE that worsened (either in severity or seriousness) or that was newly developed after the Part 1 TE period if subjects who did not receive study drug in Part 2 or after the Part 2 Safety Period if subjects received study drug in Part 2.

For the overview of all TEAEs during the Part 2 Safety Period (as defined in Section 9.2.3.1), the frequency counts and percentages will be summarized.

For the summary tables of TEAEs during the Part 2 Safety Period, the frequency counts and percentages will be presented by MedDRA SOC and PT.

In addition, TEAEs during the Part 2 Safety Period and post-treatment AEs will be presented in an individual subject data listing based on the Safety Set, Part 2.

Similar as the Part 1 analysis of AESIs, the treatment-emergent elevated transaminases events and respiratory events during the Part 2 Safety Period will be summarized.

9.3.3.2 Clinical Laboratory and Vital Signs

For the treatment-emergent laboratory and vital sign assessments during the Part 2 Safety Period, the observed values and change from the LUM/IVA baseline values will be summarized at each Part 2 visit and presented by treatment sequence.

For the treatment-emergent clinical laboratory, the number and percentage of subjects meeting at least 1 threshold analysis criterion during the Part 2 Safety Period will be summarized. The threshold analysis criteria are provided in [Appendix D](#).

[figure not shown]
In addition, a listing containing individual subject hematology and chemistry values and a listing containing individual subject vital signs values during the study Part 2 will be provided. Both listings will include data from both scheduled and unscheduled visits.

9.3.3.3 Ophthalmologic Examination

The OE results during the Part 2 Safety Period will be presented in individual subject data listings.

9.3.3.4 Physical Examination

Abnormal PE findings will be presented as an individual subject data listing only as appropriate.

10 DMC ANALYSIS

An independent data monitoring committee (DMC) was formed before initiation of this study. The DMC's objectives and operational details are described in a separate document (DMC Charter) which was finalized before the first subject was screened in the study. The DMC will conduct planned safety reviews of study data as outlined in the DMC Charter and DMC Statistical Analysis Plan.

12 LIST OF APPENDICES

Appendix A: Analysis Visit Windows for Safety and Efficacy Assessment

[figure not shown]
Table 12-1 Analysis Visit Windows for Safety and Efficacy Assessments

Assessment	Visit ¹	Target Study Day	Analysis Visit Window ^{2,3,4,5} (in study Part 1 or 2 days)
Safety Assessment			
Serum Chemistry	Day 1 (Study Baseline) Day 15 Week 12 Week 24 Week 36 Week 48	1 15 85 169 253 337	≤1 Pre-dose [1, 49] [50, 126] [127, 210] [211, 294] [295, min(337+67, 1 st dose of Part 2)]
	Day 350 Week 60 Week 72 Week 84 Week 96 Safety Follow-up	Part 2 Day 15 Part 2 Day 85 Part 2 Day 169 Part 2 Day 253 Part 2 Day 337 N/A	[1 st dose of Part 2, 49] [50, 126] [127, 210] [211, 294] [295, 337+67] Use nominal visit
Hematology	Day 1 (Study Baseline) Week 12 Week 24 Week 36 Week 48	1 85 169 253 337	≤1 Pre-dose [1, 126] [127, 210] [211, 294] [295, min(337+67, 1 st dose of Part 2)]
	Week 60 Week 72 Week 84 Week 96 Safety Follow-up	Part 2 Day 85 Part 2 Day 169 Part 2 Day 253 Part 2 Day 337 N/A	[1 st dose of Part 2, 126] [127, 210] [211, 294] [295, 337+67] Use nominal visit
Vital signs (excluding Weight and Stature)	Day 1 (Study Baseline) Day 15 Week 12 Week 24 Week 36 Week 48	1 15 85 169 253 337	≤1 [1, 49] [50, 126] [127, 210] [211, 294] [295, min(337+67, 1 st dose of Part 2)]
	Day 350 Week 60 Week 72 Week 84 Week 96 Safety Follow-up	Part 2 Day 15 Part 2 Day 85 Part 2 Day 169 Part 2 Day 253 Part 2 Day 337 N/A	[1 st dose of Part 2, 49] [50, 126] [127, 210] [211, 294] [295, 337+67] Use nominal visit
Efficacy Assessment			

Table 12-1 Analysis Visit Windows for Safety and Efficacy Assessments

Assessment	Visit ¹	Target Study Day	Analysis Visit Window ^{2,3,4,5} (in study Part 1 or 2 days)
MRI	Day 1 (Study Baseline) Week 48	1 337	≤1 Pre-dose (1, min(337+67, 1 st dose of Part 2)]
	Week 96	Part 2 Day 337	[1 st dose of Part 2, 337+67]
MBW [REDACTED]	Day 1 (Study Baseline) Week 12 Week 24 Week 36 Week 48	1 85 169 253 337	≤1 Pre-dose (1, 126] [127, 210] [211, 294] [295, min(337+67, 1 st dose of Part 2)]
	Week 60 Week 72 Week 84 Week 96	Part 2 Day 85 Part 2 Day 169 Part 2 Day 253 Part 2 Day 337	[1 st dose of Part 2, 126] [127, 210] [211, 294] [295, 337+67]
Weight and Stature	Day 1 (Study Baseline) Day 15 Week 12 Week 24 Week 36 Week 48	1 15 85 169 253 337	≤1 Pre-dose [1, 49] [50, 126] [127, 210] [211, 294] [295, min(337+67, 1 st dose of Part 2)]
	Day 350 Week 60 Week 72 Week 84 Week 96	Part 2 Day 15 Part 2 Day 85 Part 2 Day 169 Part 2 Day 253 Part 2 Day 337	[1 st dose of Part 2, 49] [50, 126] [127, 210] [211, 294] [295, 337+67]

Notes:

¹Visit name for analysis purpose is used to report data in tables and figures.

²The analysis visit windows will be applied using the following rules for both scheduled and unscheduled visits:

- a. If no numerical measurement is available within a visit window, the measurement will be considered missing for the visit.
- b. If there is more than 1 numerical measurement available within a visit window, use the following rules:
 - i. The measurement closest to the target day will be used; or
 - ii. If there are multiple measurements with the same distance from the target day, the latest measurement will be used.

Table 12-1 Analysis Visit Windows for Safety and Efficacy Assessments

Assessment	Visit ¹	Target Study Day	Analysis Visit Window ^{2,3, 4, 5} (in study Part 1 or 2 days)

³ For lab and vital sign measurement collected on the date of first dose of study drug in Treatment Period (Part 1 or Part 2 of study), if it cannot be determined whether the measurement is before or after the first dose:
 
 Scheduled measurement will be treated as pre-dose observation. Unscheduled measurement will be treated as post-dose observation. 
⁴ For safety assessment, Safety Follow-up analysis visit will be based on nominal Safety Follow-up visit. If a subject doesn't have a nominal Safety Follow-up visit but has an ETT visit with study day >680, then the ETT visit will be mapped into Safety Follow-up analysis visit.
 
Derived Variables:
 
 Age (in years) at first dose date and nominal visit (for demographics and listing variables): Obtain the age at informed consent (in days) in "yy, mm" format (e.g., 24 years, 6 months) from the Vital Signs (VS) page at the Screening Visit and add 0.5 month to convert to days. Obtain the informed consent date. Then age (in years) at first dose or nominal visit = [(first dose date or nominal visit date – informed consent date) in days + age at informed consent (in days)]/365.25. Age (in months) at nominal visit (for use in calculation of BMI, stature z-score, and weight z-score): Obtain the age at informed consent (in months) in "yy, mm" format (e.g., 24 years, 6 months) from Vital Signs (VS) page at the Screening Visit. Obtain the informed consent date. Then age (in months) at nominal visit = integer part of {(age at informed consent (in months) + 0.5 + diff(first dose date or nominal visit date, informed consent date) in months)} + 0.5. Missing first dose date or last dose date If the first dose date is missing, use Day 1 visit date to impute. If the last dose date is missing or partial date is reported, the last dose date will be imputed based on, in descending order priority, the Early Treatment Termination (ETT) visit date, last visit date before the Safety Follow-up, or the last study drug administration date from EX SDTM domain, as appropriate. The imputation algorithm will ensure the imputed last dose date does not exceed the study participation end date. 

 
 The 1st dose of Part 2: The analysis visit window of the study Part 1 is ended at the day of Week 48 visit before the 1st dose of Part 2. The analysis visit window of the study Part 2 is started from the day of Week 48 visit after the 1st dose of Part 2. Post-dose Vital signs: The analysis window for post-dose vital sign measures will be 1 hour (± 15 minutes), 2 hours (± 15 minutes), and 4 hours (± 15 minutes). Any measures after the last post-dose analysis window will be allocated to the next analysis window. 			

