**Table 3-2 Study VX16-809-121: Treatment Period and Safety Follow-up Visit**

Event/Assessment a	Treatment Period									ETT Visit b	Safety Follow-up Visit c
	Part 1: Placebo-controlled Period				Part 1/ Part 2 d	Part 2: Open-label Period e					
	Day 1	Day 3 (± 1 Day)	Day 15 (± 3 Days)	Weeks 12, 24, 36 (± 7 Days)	Week 48 (± 7 Days)	Day 338 f (± 1 Day)	Day 350 (± 3 Days)	Weeks 60, 72, 84 (± 7 Days)	Week 96 (± 7 Days)		
Abbreviated PE	X p				X p						
Serum chemistry q,r	X		X	X	X		X	X	X	X	X
Hematology q,r				X	X			X	X	X	X
MBW v	X			X	X			X	X	X	X
MRI	X w				X w,x				X w,w	X	

p An abbreviated PE will be performed 4 hours (± 30 minutes) postdose on Day 1 and at Week 48 (Section 11.5.4).

q Refer to Section 11.5.2 for details.

r If the MRI occurs before the scheduled study visit, this assessment may occur on the same day as the MRI assessment. Blood draws performed on the same day as the MRI assessment must be collected before administration of any medications related to MRI procedures.

v The MBW assessment should be performed pre-bronchodilator and before dosing. The assessment will be performed in multiple replicates. Refer to Section 11.4.2 for details.

w Subjects may complete the imaging assessment up to 7 days before the scheduled visit. Screening assessments must be completed, inclusion and exclusion criteria must be reviewed, and subjects must meet eligibility criteria relevant at the time before participating in the baseline MRI assessment up to 7 days before Day 1. If the MRI is performed before the scheduled visit, the blood draws for serum chemistry, hematology, and ██████████ may be performed on the day of the MRI assessment. Blood draws for any assessment performed on the same day as MRI testing must be collected before administration of any medications related to MRI procedures. ██████████

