x The MRI at Weeks 48 and/or 96 may be delayed for up to 60 days if the subject is recovering from a PEx. The MRI should be done after the PEx is resolved and at least 28 days after the last dose of the antibiotic regimen for the treatment of pulmonary infection has been completed. If the 28-day antibiotic-free period is not completed before the 60-day extension ends, the MRI should be completed within 1 week of the end of the 60-day extension. If the MRI at Weeks 48 and/or 96 is delayed, all other assessments must also be delayed.

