### 12.3.3 Efficacy Analysis

All efficacy analyses described in this section will be based on the FAS, unless specified otherwise. The analysis will include all available measurements through the last scheduled on-treatment visit, including measurements after treatment discontinuation.

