8.1 Part 1 Efficacy Analysis Period

The **Part 1 Efficacy Analysis Period** will include the time from the first dose date of study drug until the last efficacy assessment in Part 1, which may be collected up to the Week 48 Visit.

[figure not shown]

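### The Day 404 limit on the Week 48 windows has room for only one of the protocol's 7-day allowances, so a few predose Week 48 values could be set to missing

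*SAP*

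**What the plan says.** **SAP Appendix A, Table 12-1.** The Week 48 MRI window has the limits "1, min(337+67, 1 st dose of Part 2". The Week 48 windows for washout, weight and stature, laboratory tests and vital signs have the same upper limit. For washout, weight, stature and chemistry the limits read "295, min(337+67, 1 st dose of Part 2". Note 2a adds: "If no numerical measurement is available within a visit window, the measurement will be considered missing for the visit". SAP 9.1 says that missing data are not imputed unless otherwise specified.

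**Protocol Table 3-2.** The Week 48 column has a tolerance of ±7 days. The Week 48 MRI cell carries two footnotes:
- Footnote w: "Subjects may complete the imaging assessment up to 7 days before the scheduled visit".
- Footnote x: "The MRI at Weeks 48 and/or 96 may be delayed for up to 60 days if the subject is recovering from a PEx". If the 28-day antibiotic-free period is still incomplete when the extension ends, "the MRI should be completed within 1 week of the end of the 60-day extension".

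All other assessments move with a delayed MRI, and study drug continues until the delayed visit is complete (footnotes x and z; Protocol 9.1.2, 9.3.2.2 and 11.1).

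**Statements without a day limit.** SAP 8.1 runs the Part 1 efficacy period "until the last efficacy assessment in Part 1, which may be collected up to the Week 48 Visit". The Appendix A note on the first dose of Part 2 closes the Part 1 window at the Week 48 visit, before that dose. Protocol 12.3.3 says: "The analysis will include all available measurements through the last scheduled on-treatment visit".

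**The concern.** The 67 days in the cap hold the 60-day delay and one further week. The protocol has three separate 7-day allowances around Week 48: the visit tolerance, the MRI before its visit, and the MRI after the extension ends. If two of them apply to the same child, a Week 48 value can come after Day 404 and still precede the first open-label dose, while the child is on randomised treatment. Table 12-1 would set that value to missing, whereas SAP 8.1, the Appendix A note and Protocol 12.3.3 would include it.

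At stake are several Week 48 values from the same child, because the assessments are delayed together. The stated reason for the delay is recovery from an exacerbation, so a link between the loss and the outcome is plausible. In a trial of about 50 children, with 17 on placebo, single observations matter.

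**Working it through.** **1. Reproduce the cap.** Target day = 1 + 48×7 = 337. Cap = 337 + 67 = 404. The protocol's rules give the same day as 337 + 60 + 7 (delay plus extra week). The sum 337 + 7 + 60 (visit tolerance plus delay, no extra week) also gives 404. Either way there is room for one 7-day allowance.

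**2. Latest permitted day under each reading.** The protocol does not state whether the 60 days run from Day 337 or from a visit within its tolerance (latest Day 337 + 7 = 344). Nor does it state whether the MRI-before-visit allowance still applies once the visit is delayed, although the Week 48 MRI cell carries both footnotes.

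| Reading | Latest MRI | Latest visit-day values | Days past 404 (MRI / visit) |
|---|---|---|---|
| A: from Day 337, MRI at the visit | 337+60+7 = 404 | 404 | 0 / 0 |
| B: as A, visit 7 days after MRI | 404 | 404+7 = 411 | 0 / 7 |
| C: from Day 344, MRI at the visit | 344+60+7 = 411 | 411 | 7 / 7 |
| D: as C, visit 7 days after MRI | 411 | 411+7 = 418 | 7 / 14 |

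**3. Where a predose value on Day 405 goes.** It is past the Week 48 limit. The Part 2 windows open only at the first dose of Part 2, which has not yet been given. It therefore falls in no window, and note 2a makes it missing.

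**4. How late the illness must be.** Counted from Day 337, the extension ends on Day 397. The extra week is needed only if antibiotics end after Day 397 − 28 = 369. Counted from Day 344, the extension ends on Day 404, and antibiotics would have to end after Day 404 − 28 = 376.

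**5. What is lost.** The primary endpoint is lost only under readings C and D. Under B to D, the three Week 48 growth z-score endpoints can be lost. LCI loses one of the four visits in its average. Laboratory data lose the by-visit Week 48 summary; threshold analyses use the Part 1 treatment-emergent period and are not tied to the window.

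**6. Sensitivity of the posterior to one lost MRI (illustration only).** Inputs from Protocol 12.1: SD 5, placebo change +3.0, LUM/IVA change +1.66. Assumptions: 29 and 15 evaluable children (33 and 17 less 10%, rounded down), the vague prior treated as flat, and the SD as known. Posterior = Φ(difference in means / SE), with SE = 5·√(1/n₁ + 1/n₂).
- No loss: SE = 5·√(1/29 + 1/15) = 1.590; Φ(1.34/1.590) = 0.80, the protocol's figure.
- One placebo child at +8 lost (one SD worse than the mean): placebo mean (45 − 8)/14 = 2.643; SE = 1.627; Φ(0.983/1.627) = 0.73.
- One LUM/IVA child at +6.66 lost (one SD worse): LUM/IVA mean (48.14 − 6.66)/28 = 1.481; SE = 1.600; Φ(1.519/1.600) = 0.83.
- One average placebo child lost: Φ(1.34/1.627) = 0.79.

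The posterior can move either way, depending on which child is lost.

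**The case against.** The strongest reply is that the cap was evidently built from the protocol's own rule. Counted from Day 337, the last permitted MRI is exactly Day 404, and no primary data are lost. Protocol 9.1.2 also speaks of extending the treatment period by up to 60 days for the Week 48 MRI, and no passage says that the count starts from a late visit. A visit on Day 418 needs every allowance used to its limit. This stands: MRI loss is conditional on an unsettled reading. It does not dispose of reading B, where the count starts at Day 337 and visit-day values still pass the cap.

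Second, the cap has a purpose. A reader might infer that it is redundant because the first dose of Part 2 already ends the window. For children who never enter Part 2 there is no such dose, and 337+67 is their only upper limit. Replacing it by a Week 48 Visit date would leave the limit undefined for a child with only an early-termination visit. This stands and shapes the fix.

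Third, other values may fill the gap. Under the Appendix A rules, an unscheduled weight or stature measurement within Days 295 to 404 would serve as the Week 48 value. This reduces the expected loss but does not remove the inconsistency.

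**Conclusion.** The point holds as an edge-case inconsistency. The Week 48 cap falls short of the protocol's combined allowances by 0 to 7 days for the MRI and 0 to 14 days for visit-day assessments. The upper ends rest on the 60 days running from Day 344 and, for the 14 days, on the MRI also preceding its visit by 7 days. Values in that gap are predose and on randomised treatment, and three other statements in the two documents would include them.

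The documents give no count of affected children. They would be few, mainly those with a prolonged exacerbation near Week 48.

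Two stronger readings are not supported. A reader might infer that the plan discards primary data from the sickest children. The plain count from Day 337 loses no MRI, and an exacerbation near Week 48 is not shown to mark overall severity. A reader might also infer a known bias in the posterior probability. The illustration gives 73% or 83% from the same 80% start, depending on the arm, so neither direction nor size is established.

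The case for acting is consistency at small cost. The MRI window already accepts any scan after Day 1 as Week 48, so there is little reason to refuse a predose scan on Day 405.

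**What to change.** 1. In every Week 48 row of SAP Table 12-1, for children who enter Part 2, end the window at the predose first dose of Part 2 and drop the Day 404 cap. This agrees with the existing Appendix A note and changes nothing for a child whose first Part 2 dose comes by Day 404.
2. For children who do not enter Part 2, keep 337+67, so that early-termination assessments stay in the window.
3. Check the Week 96 limit (Part 2 Day 337+67 = 404) against the same allowances.
4. Reconcile the protocol passages (Table 3-2 footnotes w and x, Protocol 9.1.2 and 11.1) on when the 60-day count starts and how the 7-day allowances combine. Items 1 and 2 do not depend on how this is settled.

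The cost is a change of table wording and a line of programming, with no new data. It should be made before the Part 1 data cut and unblinding.

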**Table 3-2 Study VX16-809-121: Treatment Period and Safety Follow-up Visit**

Event/Assessment a	Treatment Period									ETT Visit b	Safety Follow-up Visit c
	Part 1: Placebo-controlled Period				Part 1/ Part 2 d	Part 2: Open-label Period e					
	Day 1	Day 3 (± 1 Day)	Day 15 (± 3 Days)	Weeks 12, 24, 36 (± 7 Days)	Week 48 (± 7 Days)	Day 338 f (± 1 Day)	Day 350 (± 3 Days)	Weeks 60, 72, 84 (± 7 Days)	Week 96 (± 7 Days)		
Clinic visit	X		X	X	X		X	X	X	X	X
Telephone contact g		X				X					
Randomization h	X										
Stature and weight i	X		X	X	X		X	X	X	X	X
Vital signs j	X k		X	X	X k		X	X	X	X	X
OE l					X m				X m,n	X m,n	X m,n
Full PE o	X			Week 24	X			Week 72	X	X	X

- a Assessments will be performed before study drug dosing unless noted otherwise (Section 11.1).
- b If the ETT Visit occurs 10 days or later after the last dose of study drug, the Safety Follow-up Visit will not be required. Subjects who prematurely discontinue study drug treatment for AEs should be followed until the AE is considered resolved.
- c The Safety Follow-up Visit is required for 1) subjects who complete their ETT Visit <10 days after the last dose of study drug and 2) subjects who interrupt study drug treatment and complete their Week 96 Visit <10 days after the last dose of study drug; it is not required for subjects who continue onto commercially available, physician-prescribed LUM/IVA within 2 weeks (± 4 days) of completing study drug treatment at the Week 96 or ETT Visit.
- d The first open-label dose of LUM/IVA will be the dose administered at the Week 48 Visit after completion of the predose assessments.
- e If the subject's Week 48 Visit is delayed, all subsequent visits must be delayed accordingly based on the actual Week 48 Visit date.
- f The Day 338 Visit (telephone contact) should occur 1 to 3 days after the actual date of the Week 48 Visit, regardless of whether it is Study Day 338.
- g Telephone contacts will be made to assess the subject's status, any AEs, medications, treatments, and procedures.
- h Randomization must only occur after all inclusion and exclusion criteria are met and before the first dose of study drug. Randomization will be done through IWRS and may occur on Day -1.

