### 9.1.2 Treatment Period

The Treatment Period is 96 weeks; study drug will be administered every 12 hours (q12h) from Day 1 through Week 96 (Section 9.1). The Treatment Period can be extended up to 60 days in the event of a PEx: up to 60 days for the Week 48 MRI, and up to 60 days for the Week 96 MRI, for a total of up to 120 days. Antibiotics taken for a pulmonary infection or exacerbation must be completed at least 28 days before the MRI scan (Section 11.1). If the 28-day antibiotic free period is not completed before the 60-day extension ends, the MRI should be completed within 1 week of the end of the 60-day extension. If the MRI at Weeks 48 and 96 is delayed, all other assessments must also be delayed.

Study visits during the Treatment Period will occur as shown in Table 3-2. Subjects will be outpatients during the Treatment Period.

Study drug administration and management details are provided in Section 9.6 and Section 10, respectively.

Procedures for subjects who prematurely discontinue treatment are described in Section 9.1.4.

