### 9.1.3 Follow-up

Subjects will have a Safety Follow-up Visit 2 weeks ( $\pm$  4 days) after the last study drug dose. Safety Follow-up Visit assessments are listed in Table 3-2.

The Safety Follow-up Visit is required for 1) subjects who complete their Early Termination of Treatment (ETT) Visit <10 days after the last dose of study drug (Section 9.1.4) and 2) subjects who interrupt study drug treatment and complete their Week 96 Visit <10 days after the last dose of study drug; it is not required for subjects who continue onto commercially available, physician-prescribed LUM/IVA within 2 weeks ( $\pm$  4 days) of completing study drug treatment at the Week 96 or ETT Visit.

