### 9.1.4 Early Termination of Treatment Early Discontinuation

If the subject prematurely discontinues study treatment, an ETT Visit should be scheduled as soon as possible after the subject decides to terminate study treatment. Subjects who prematurely discontinue treatment may also be required to complete the Safety Follow-up Visit, approximately 2 weeks ( $\pm$  4 days) after their last dose of study drug (Section 9.1.3). The assessments performed at the Safety Follow-up Visit are listed in Table 3-2.

If the ETT Visit occurs  $\geq$ 10 days following the last dose of study drug, then the ETT Visit will replace the Safety Follow-up Visit, and a separate Safety Follow-up Visit will not be required.

Subjects who prematurely discontinue study drug treatment for adverse events (AEs) should be followed until the AE is considered resolved.

Subjects who become eligible to receive commercially-available LUM/IVA by prescription of a physician, and who choose to continue onto commercially-available LUM/IVA before completion of the study, must remain on study-supplied drug through the ETT Visit, and may only initiate treatment with commercially-available LUM/IVA after completion of this visit.

If the subject withdraws consent for the study, no further evaluations should be performed, and no additional data should be collected. Vertex may retain and continue to use any data and samples collected before such withdrawal of consent.

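### SAP Appendix A note 4 maps an ETT visit to Safety Follow-up by study day (>680) instead of time since last dose, so some visits are mislabelled in descriptive by-visit safety tables

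*SAP*

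**What the plan says.** **SAP, Appendix A, note 4.** For safety assessments, the "Safety Follow-up analysis visit will be based on nominal Safety Follow-up visit". One exception follows. If a child has no such visit but "has an ETT visit with study day >680, then the ETT visit will be mapped into Safety Follow-up analysis visit". The note does not refer to the date of last dose.

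**Protocol, Section 9.1.4.** When the ETT Visit falls at least 10 days after the last dose, "then the ETT Visit will replace the Safety Follow-up Visit, and a separate Safety Follow-up Visit will not be required". Table 3-2, footnote b, agrees: "If the ETT Visit occurs 10 days or later after the last dose of study drug, the Safety Follow-up Visit will not be required". Section 13.1.1.3 uses the same 10-day criterion to close adverse-event collection. None of these depends on study day.

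**Children who switch to commercial drug.** Under protocol Section 9.1.4 they "must remain on study-supplied drug through the ETT Visit". Section 9.1.3 says of the Safety Follow-up Visit that "it is not required for subjects who continue onto commercially available, physician-prescribed LUM/IVA within 2 weeks" (± 4 days) of completing study treatment.

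**Delays.** Protocol Section 9.1.2 lets the Treatment Period be extended for a pulmonary exacerbation by "up to 60 days for the Week 48 MRI". If the antibiotic-free period is still incomplete by then, "the MRI should be completed within 1 week of the end of the 60-day extension". Table 3-2, footnote e, moves all later visits with the actual Week 48 Visit. SAP Table 12-1 follows this by windowing Part 2 on Part 2 days.

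**The concern.** Note 4 exists because some ETT visits are in effect follow-up visits. What makes them so is time off drug, and that is what the protocol uses. A fixed calendar day is a poor substitute in two ways.

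- **(a) Off-drug visits shown as treatment weeks.** A child who stops early has the ETT visit well before Day 681. If it is 10 or more days after the last dose, it replaces Safety Follow-up under the protocol, but the SAP puts it in a treatment-week window.
- **(b) On-drug visits shown as follow-up.** The Part 2 windows move with a delayed Week 48 Visit, but Day 680 does not. A delayed child can be past Day 680, still on drug and weeks from Week 96.

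At stake is whether the by-visit laboratory and vital-sign summaries (SAP 9.2.3.2, 9.2.3.3 and 9.3.3.2) show what their visit labels say.

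**Working it through.** **Inputs**

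- Week 48 target: Day 337. Week 96 target: Part 2 Day 337 (SAP Table 12-1).
- Week 96 visit window: ± 7 days (protocol Table 3-2).
- Longest Week 48 delay: 60 + 7 = 67 days (protocol 9.1.2; the SAP windows use 337+67).
- Laboratory and vital-sign windows: Week 36 is [211, 294] in Part 1; Week 84 is [211, 294] and Week 96 is [295, 404] in Part 2 days.
- Treatment-emergent and Part 2 Safety Periods end no later than 14 days after last dose (SAP 8.2, 8.4).
- Safety Follow-up is due 14 ± 4 days after last dose, so 10 to 18 days (protocol 9.1.3).

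I read study day as the overall study day, because the Part 2 windows end at Part 2 Day 404.

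**The plan's figure.** Week 96 is 96 × 7 + 1 = Day 673, and 673 + 7 = 680. The cut-off is the end of the undelayed Week 96 window.

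**(a) Off-drug ETT visits**

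1. Take last dose on Day 200 and ETT on Day 212, which is 12 days off drug. The protocol lets this visit replace Safety Follow-up.
2. Day 212 is not above 680, so note 4 does not apply. The visit falls in [211, 294] and is labelled Week 36.
3. The treatment-emergent period runs to at most Day 200 + 14 = Day 214, so the value is included. If it is the only value in that window, it becomes the child's Week 36 result.
4. By note 4, a nominal Safety Follow-up visit 12 days off drug is labelled Safety Follow-up. The same time off drug gets two labels.
5. After a Part 1 stop, the last dose is on Day 404 at the latest. An ETT 14 days later is on Day 418, so no prompt Part 1 ETT can reach Day 681.

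More generally, let the Week 48 delay be d days and the ETT be g days after last dose. Note 4 applies only if the last dose is on Day 681 − g or later. Of the 672 + d last-dose days before the Week 96 target, that is d + g − 8 days:

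| d | g | Mapped | Share |
|---|---|---|---|
| 0 | 10 | 2 of 672 | 0.3% |
| 0 | 14 | 6 of 672 | 0.9% |
| 67 | 10 | 69 of 739 | 9.3% |
| 67 | 14 | 73 of 739 | 9.9% |

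These are shares of possible last-dose days, not predicted shares of children.

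**(b) On-drug ETT visits after a delayed Week 48**

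Part 2 Day 1 is study Day 337 + d. Study Day 681 is then Part 2 Day 681 − (337 + d) + 1 = 345 − d. The Week 96 target is study Day 673 + d. The number of days from Day 681 up to the day before that target is d − 8, or 0 if negative.

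| Delay d | Part 2 Day 1 | Day 681 is Part 2 Day | Window | Week 96 target | Days exposed |
|---|---|---|---|---|---|
| 0 | 337 | 345 | Week 96 | 673 | 0 |
| 7 | 344 | 338 | Week 96 | 680 | 0 |
| 28 | 365 | 317 | Week 96 | 701 | 20 |
| 60 | 397 | 285 | Week 84 | 733 | 52 |
| 67 | 404 | 278 | Week 84 | 740 | 59 |

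An ETT on an exposed day, with no nominal Safety Follow-up visit, is labelled Safety Follow-up. Children switching to commercial drug meet that condition while on study drug.

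**The case against.** The strongest reply is that little depends on the label.

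- **Period limit.** The by-visit summaries cover only treatment-emergent data, so a value more than 14 days off drug is already outside them. A reader might infer that off-drug values are wrongly let into the on-treatment data. The documents do not support that: the SAP counts the 14 days after last dose by design. Only the visit label is at issue. This stands.
- **Closest-value rule.** Under note 2 of the same appendix, the measurement nearest the target day is used. An ETT late in a window that already holds the scheduled visit would not be tabulated. This narrows (a) further.
- **Liver signals.** A reader might infer that children who stop for raised transaminases are most affected. The documents give no basis for that. Threshold counts run over the whole period, adverse-event and special-interest tables use event dates and terms, and all values are listed.
- **Conditions for (b).** The protocol requires Safety Follow-up when the ETT is under 10 days from last dose, unless the child switches to commercial drug. So (b) needs a delay of more than about a week, an ETT after Day 680, and a switch or a missed required visit. This stands, and the 67-day case is the extreme.
- **Purpose of the protocol text.** It decides whether a visit takes place, not how it is labelled in tables. That is fair, but it says the ETT replaces Safety Follow-up, and the SAP gives no reason for another criterion.
- **Redaction.** Part of Appendix A is blacked out and might add detail. Note 4 reads as complete where printed.

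**Conclusion.** Note 4 uses the wrong criterion and should be reconciled with protocol Section 9.1.4 and Table 3-2. Followed as written, it mislabels visits in both directions. It misses nearly all off-drug ETT visits, though not every one, since those after Day 680 are still mapped.

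The consequence is small. It is confined to descriptive by-visit laboratory and vital-sign summaries: in (a) to values about 10 to 14 days off drug, in (b) to a few delayed children. Threshold counts, adverse-event tables, listings and the primary endpoint do not use the mapping.

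The number of children cannot be derived. A reader might apply the planned 10% dropout rate to 50 subjects and infer about five. That would assume every dropout has an ETT at least 10 days off drug, whereas the protocol asks for the ETT as soon as possible and keeps switchers on drug through it. The number is probably small.

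The conclusion assumes that study day means overall study day and that no redacted text changes note 4.

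**What to change.** 1. In note 4, replace the study-day condition with: ETT visit 10 or more days after the last dose of study drug. Keep the condition that there is no nominal Safety Follow-up visit.
2. Keep the rule to safety assessments, as note 4 already does. Protocol Section 12.3.3 deliberately includes efficacy measurements after treatment discontinuation.
3. Add a Safety Follow-up row to the Part 1 safety windows in Table 12-1, which now lists one only after Week 96. Tabulate each such visit there and not in a treatment-week window.
4. Keep these values in the treatment-emergent period for the threshold and adverse-event analyses.
5. Use the recorded last-dose date. Appendix A imputes a missing one first from the ETT date, which gives zero days off drug, so the new rule would not apply.

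The cost is a few lines of SAP wording and some table programming. No new data are needed where the last-dose date is recorded.
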